11.1.4 Device Deficiencies

Device Deficiencies means any inadequacy of a medical device with respect to its identity, quality, durability, reliability, safety or performance

11.2 Documentation

11.2.1 (Serious) Adverse Events / Adverse Device Effects

Independent from a possible relation to the investigational device, every AE spontaneously reported by the subject or observed by the investigator has to be reported on the appropriate page of the case report form. Furthermore, the investigator shall actively ask the subject about the occurrence of any (S)AE at each visit and note any abnormal laboratory findings. For each adverse event the following information should be documented:

- Description of the event (diagnosis and symptoms in verbatim terms),
- Outcome,
- Seriousness,
- Duration (start date and stop date),
- Causal relationship to the investigational device.

Causality assessment will be done by the investigator using a 5-category system (no related / unlikely / possible / probable / causal relationship).

- Any therapy or corrective action initiated including.

The results of any complementary tests performed (laboratory tests, ECG, etc.) must be pseudonymized by the investigator prior to forwarding information to the sponsor. A period of 4 weeks for follow up of AEs after the subject has routinely completed or prematurely terminated the study seems sufficient. This means that any additional information needed to assess the (S)AE should be collected and documented in the respective CRF within one month after occurrence.

11.2.2 Device deficiencies

Two device deficiencies of the disposable Spiral Segment were documented in previous clinical studies with PowerSpiral. The technical issues are addressed and solved.

11.3 Reporting Responsibilities

11.3.1 Serious Adverse Events (SAE) / Serious Adverse Device Effects (SADE)

After the signature on the consent form is obtained, any SAE occurring while the subject is enrolled in the study must be immediately reported by the investigator.

Clinical Investigation Plan

CIP Reference No.:2018-GI (OEKG) -01. The **SAMISEN** study - Final Version 02 - Date 23th April 2019

11.3.1.1 Serious Adverse Event - Initial Report

The investigator has to report every SAE immediately after he/she becomes aware of the SAE.

The Sponsor compile an accumulated SAE list and share with Ethical Committees on a bi-annual basis (if requested by the respective Ethical Committees). However, for international safety reporting requirements the sponsor needs to be informed immediately about any observed SAE.

11.3.1.2 Serious Adverse Event - Follow-up Report

If the event / SAE is not resolved further information (e.g. laboratory reports, surgical reports) for full assessment is needed and shall be provided as soon as it becomes available. The sponsor may request additional documents, shall be provided within 5 days.

11.3.2 Device deficiencies

Device deficiencies shall be reported to the sponsor not later than 7 working days after observation.

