5 DATA MANAGEMENT

5.1 Data recording

Data shall be recorded in the eCRFs in a timely manner but not later than 5 working days after collection of the data, including signatures. Please take into account, a SAE must be documented immediately to meet the reporting requirements. The investigator must document all visits and assessments on the respective eCRF form and shall ensure that no empty data blocks exist. If a test or assessment was not performed, the investigator shall indicate this. If a question does not apply, the investigator shall also document this (e.g. by entering "NA").

The investigator shall sign the overall affirmation statement for each patient to document personal responsibility for accuracy, completeness of data captured in the system and for the trial being carried out according to the protocol and any amendments.

Data can only be entered by authorized and trained site staff, i.e. by the investigator or investigator's staff trained on eCRF procedures. (S)AE pages must be signed off by the investigator.

Data corrections in the eCRF done by the investigator or designee require entering a reason for the data change. The change of already entered data and the person who performed the data change will be tracked in the audit trail of the eCRF. In case of data changes in the eCRF that has already been signed off a new signature is required to authorize the data modification.

Queries issued within the eCRF shall be answered within 7 working days.

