11.1.2 Adverse Device Effect (ADE)

An ADE is an adverse event related to the use of an investigational medical device.

Note:

- This definition includes any adverse event resulting from insufficiencies or inadequacies in the instructions for use, the deployment, the implantation, the installation, the operation, or any malfunction of the investigational medical device.
- This definition includes any event that is a result of a use error or intentional misuse.
- This includes medical devices already on the market that are being evaluated for unintended uses, new populations, new materials or design changes.

Clinical Investigation Plan

CIP Reference No.:2018-GI (OEKG) -01. The **SAMISEN** study - Final Version 02 - Date 23th April 2019

11.1.3 **Serious Adverse Event / Serious Adverse Device Effect (SAE /SADE)**

A SAE/SADE is further specified by the fact that it results or could have resulted in death or severe deterioration of health of a subject, user, or other persons, whether (SADE) or not (SAE) related to the investigational medical device.

The criteria for a Serious Adverse Event (SAE) are the following:

- Led to a death,
- Led to a serious deterioration in health of the subject, that either resulted in:
 - A life-threatening illness or injury, or
 - A permanent impairment of a body structure or a body function, or
 - In-patient or prolonged hospitalization, or
 - In medical or surgical intervention to prevent life threatening illness or injury or permanent impairment to a body structure or a body function,
- Led to fetal distress, fetal death or a congenital abnormality or birth defect.

Note: Planned hospitalization for a pre-existing condition, or a procedure required by the CIP, without serious deterioration in health, is not considered a serious adverse event.

The following points should be taken into account when evaluating the seriousness of an Adverse Event:

- The life-threatening criterion indicates that there was an immediate risk of death at the time of its occurrence. This does not mean that if the adverse event had occurred in a more severe form it would have led to death.
- The following events are not considered to be serious adverse events:
 - An event causing a brief visit to a hospital consultation, an open-door or day hospital.
 - Outpatient treatment in the emergency department although the reason for which this treatment was instituted may be serious.

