13 SUSPENSION OR PREMATURE TERMINATION

Certain circumstances may lead to early termination of an entire clinical investigation, in particular for ethical or safety reasons such as:

- The high frequency and/or unexpected severity of adverse events.
- Unsatisfactory recruitment of subjects as far as their quantity or quality is concerned or recurrent incomplete/inappropriate collection of data.

The decision to put a study on hold or for premature termination will be made by the Sponsor.

Clinical Investigation Plan

CIP Reference No.:2018-GI (OEKG) -01. The **SAMISEN** study - Final Version 02 - Date 23th April 2019

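### Protocol 11.3.2 allows every device deficiency up to 7 working days to reach the sponsor, and does not say whether one that could have led to a serious adverse event belongs on the immediate clock

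*Protocol*

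**What the plan says.** **Device deficiencies.** Section 11.1.4 of the protocol defines a device deficiency as any inadequacy of the device, safety included, and does not grade deficiencies by their potential for harm. Section 11.3.2 sets one limit for all of them: "Device deficiencies shall be reported to the sponsor not later than 7 working days after observation". Section 3.1.3 says that deficiencies must be documented and makes them part of the combined main safety endpoint. Section 11.2.2, which carries the same heading under Documentation, gives only history. Table 2 has no row for deficiencies.

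**Serious adverse events.** Section 11.3.1.1 states: "The investigator has to report every SAE immediately after he/she becomes aware of the SAE". Section 5.1 agrees for the eCRF: "a SAE must be documented immediately to meet the reporting requirements".

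**What counts as serious.** The opening sentence of section 11.1.3 says that an SAE or serious adverse device effect (SADE) is marked by the fact that "it results or could have resulted in death or severe deterioration of health of a subject, user, or other persons". The criteria list beneath it names only events that did lead to death, serious deterioration or fetal harm. Section 11.1.1 defines an adverse event as an untoward medical occurrence, disease, injury or clinical sign.

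**Who acts on a signal.** Section 13 states: "The decision to put a study on hold or for premature termination will be made by the Sponsor". Section 11.5 says that a data monitoring committee is not applicable.

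**The concern.** A malfunction that has injured nobody yet is one of the earliest signals that this registry can give about the device. The study runs alongside the European launch (section 1.2), and all devices used are identical (section 3.2.1), so a fault seen at one site may be present at the others.

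The protocol gives the hold decision to the sponsor and names no other body for it. A report that is still at the site cannot inform that decision. If a site takes a near miss to be a device deficiency only, the text allows it to keep the report for up to 7 working days. Another site that relies on the opening sentence of 11.1.3 would report the same malfunction at once. Both would be following a defensible reading of the protocol.

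**Working it through.** **1. Which clock applies.** Three kinds of malfunction, read against the definitions:

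| Malfunction | Adverse event (11.1.1)? | Opening sentence of 11.1.3 | Criteria list of 11.1.3 | Clock |
|---|---|---|---|---|
| A. Serious harm followed | Yes | Met | Met | Immediate; no doubt |
| B. Minor untoward sign, could have been serious | Yes | Met | Not met | Immediate on the opening sentence; 7-working-day limit on the list |
| C. No medical occurrence, could have been serious | No, read strictly | Met if read alone | Not met | Immediate only if the opening sentence is read alone; otherwise the 7-working-day limit |

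All three are also device deficiencies under 11.1.4. In rows B and C the answer turns on which part of 11.1.3 the site follows. No section says which part governs, and 11.3.2 does not refer to 11.3.1.1.

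The note on the life-threatening criterion in 11.1.3 leans towards the list: it asks for a risk present at the time and sets aside reasoning from a more severe form of the event. It covers that one criterion only and does not settle the matter.

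**2. Length of the limit.** The assumption is a Monday-to-Friday working week without public holidays.

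| Day of observation | 7 working days, in calendar days |
|---|---|
| Monday, Tuesday, Wednesday | 9 |
| Thursday, Friday | 11 |
| Saturday | 10 |
| Sunday | 9 |

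The range is 9 to 11 calendar days.

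**3. Patients treated in that time, as an upper bound.** Inputs: about 335 patients including learning-curve cases (section 3.3.6), an enrolment period of one year taken as 52 weeks (trial summary), and 12 sites.

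- Accrual: 335 / 52 = 6.44 patients per week.
- Over 9 days: 6.44 × 9/7 = 8.3 patients.
- Over 11 days: 6.44 × 11/7 = 10.1 patients.
- Per site: 8.3 / 12 = 0.69 to 10.1 / 12 = 0.84 patients.

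Optional second procedures are not counted. The figures assume even accrual over time and sites. They are avoidable exposure only if the site reports on the last permitted day and the sponsor would hold all sites on receipt.

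**The case against.** **The deadlines do not conflict.** A reader might infer that a near miss carries two incompatible deadlines. The documents do not support that. Seven working days is an outer limit, and an immediate report satisfies both 11.3.2 and 11.3.1.1. Once an event is accepted as an SAE, a site that waits breaches 11.3.1.1. The open question comes before that, in classification. This objection stands, and it limits the point to a gap.

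**It is not the slowest clock in the plan.** That inference is also wrong. Section 5.1 allows 7 working days for query answers, and section 11.2.1 allows one month for further information on an adverse event.

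**The comparison with routine data is weak.** Section 5.1 says: "Data shall be recorded in the eCRFs in a timely manner but not later than 5 working days after collection of the data". That is 2 working days shorter, but it governs eCRF entry after collection, whereas 11.3.2 governs notice to the sponsor after observation. These are different acts, and nothing here rests on the difference. In row B the minor adverse event itself must go on the case report form (section 11.2.1), so the sponsor may see part of the story sooner.

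**The earlier deficiencies add little.** Section 11.2.2 records two deficiencies of the disposable spiral segment in previous studies, but also says that the issues have been solved.

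**Other safeguards exist.** An investigator can discontinue a subject (section 3.3.3) and may deviate from the protocol in an emergency to protect safety (section 7). Section 9.1 refers regulatory reporting duties to the Clinical Trial Agreements, which are not among the documents and may or may not cover deficiencies. Local action, however, does not alert the other sites.

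**Nothing shows that 7 working days is wrong in general** for a CE-marked device in routine use. That stands too. The point concerns only deficiencies with serious potential.

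**Conclusion.** The point holds as a classification and precedence gap. Section 11.3.2 gives every device deficiency up to 9 to 11 calendar days, without an exception for serious potential, and 11.1.3 is inconsistent about whether such an event is an SAE/SADE. A site that follows the criteria list can hold a potentially serious malfunction for that long while remaining within the protocol.

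The size is modest. The 8 to 10 patients study-wide are an upper bound under the assumptions stated above, and at the reporting site the figure is below one patient. Actual delay would be shorter wherever sites report before the limit. The SAP's sample size and analysis method do not change. This is a cheap improvement, not a threat to the study's conclusions.

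**What to change.** 1. Reconcile the opening sentence of 11.1.3 with its criteria list, so that the protocol says plainly whether an event with only the potential for serious harm is an SAE/SADE.
2. Add to 11.3.2 that a device deficiency that could have led to an SAE/SADE is reported on the immediate clock of 11.3.1.1, through the existing SAE route. All other deficiencies stay as they are.

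The second change sets a reporting time and need not make a near miss an SAE in the analysis. The first change does decide that. The sponsor should make it knowingly, because any event classed as serious enters the SAE rate in section 3.7.1 of the SAP.

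The cost is an edit to 11.1.3, one sentence in 11.3.2 and a line in site training. The downside is a few more immediate reports.

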11.3.3 Responsible Nominated Safety Contact

11.4 Anticipated Adverse Events

Foreseeable risks include those typically associated with deep enteroscopy performed under general anesthesia or sedation.

The following device and process related events were observed in previous Investigator-Initiated-Trials with PowerSpiral. The SAMISEN study will contribute and extend the safety profile of the PowerSpiral device.

Clinical Investigation Plan

CIP Reference No.:2018-GI (OEKG) -01. The **SAMISEN** study - Final Version 02 - Date 23th April 2019

Table 4 List of anticipated (Serious) Adverse Events

- mucosal damage
- mucosal abrasion
- mucosal inflammation
- bleeding
- hematoma
- perforation
- infection
- pain (such as abdominal pain and sore throat)
- abdominal distention
- discomfort (such as abdominal discomfort and swallowing discomfort)
- digestive dysfunction (such as indigestion, nausea, vomiting)
- cardiovascular problem (bradycardia, tachycardia, hypotension and hypertension)
- dysphagia (such as odynophagia)
- respiratory system disorder (such as aspiration pneumonia, cough, hypoxemia and mediastinal emphysema)
- pancreatitis
- fever
- hyperamylasemia
- hyperlipasemia
- intestinal obstruction
- intestinal necrosis
- intussusception
- parotitis
- hiccup
- electrification
- burn
- foreign body retention
- intoxication
- gas embolism
- mucosal paratripsis
- cut

11.5 Data Monitoring Committee

Not applicable.

Clinical Investigation Plan

CIP Reference No.:2018-GI (OEKG) -01. The **SAMISEN** study - Final Version 02 - Date 23th April 2019

12 VULNERABLE POPULATION

It is not planned to include a vulnerable population.

Clinical Investigation Plan

CIP Reference No.:2018-GI (OEKG) -01. The **SAMISEN** study - Final Version 02 - Date 23th April 2019

13 SUSPENSION OR PREMATURE TERMINATION

Certain circumstances may lead to early termination of an entire clinical investigation, in particular for ethical or safety reasons such as:

- The high frequency and/or unexpected severity of adverse events.
- Unsatisfactory recruitment of subjects as far as their quantity or quality is concerned or recurrent incomplete/inappropriate collection of data.

The decision to put a study on hold or for premature termination will be made by the Sponsor.

Clinical Investigation Plan

CIP Reference No.:2018-GI (OEKG) -01. The **SAMISEN** study - Final Version 02 - Date 23th April 2019

14 PUBLICATION POLICY

The sponsor is explicitly committed to publish the trial results in a scientific medical journal and / or presented at scientific meetings. The Investigator agrees that any publication by the Study Site of study results conducted at their study site shall not be made before the first multicenter publication and as agreed between the sponsor and the Coordinating Clinical Investigator.

For greater certainty, it is hereby recalled that in its capacity as sponsor of the trial, Olympus Europa SE & Co. KG is solely responsible to co-ordinate the publications of multicenter clinical trials in order to ensure that the related results are reported in a coherent and responsible manner so that results from clinical trial data subsets are not published in advance of or without clear reference to the primary publication and/or do not repeat such primary publication. Olympus Europa SE & Co. KG decides about the nomination of investigators as authors on the basis of its internal policies, requirements of the publishers and generally accepted standards of authorship. Therefore, Olympus Europa SE & Co. KG shall be duly informed of any publication plans in order to review any proposed manuscript before submission for publication.

Clinical Investigation Plan

CIP Reference No.:2018-GI (OEKG) -01. The **SAMISEN** study - Final Version 02 - Date 23th April 2019

16 STUDY TIMELINE

Screening period	May/June 2019 – May/June 2020
Recruitment period:	May/June 2019 – May/June 2020
Database lock	July 2020
Data Review Meeting	July 2020
Statistical analysis:	July 2020
First data available	August 2020
Draft report:	November 2020
Final CIR	December 2020

Clinical Investigation Plan

CIP Reference No.:2018-GI (OEKG) -01. The **SAMISEN** study - Final Version 02 - Date 23th April 2019

17 ANNEX 01: DEEP ENTEROSCOPY PROCEDURE

17.1 General Information

A lack of frequent stalling of the rotation should be interpretive as a warning to assess the patient and scope position.

Continued rotation without advancement should also be seen as maximum insertion depth.

The limit function does not guarantee the safety of the procedure. The operator must judge if safe insertion can be continued on a case-by-case basis.

The LIMIT Function?

The limit function stops the rotation of the single use PowerSpiral tube when the electric current to the motor on the endoscope a setting value. To release, remove your foot from the pedal on foot switch.

17.2 General Insertion tips

Gentle forward pressure is used when rotation is started as well as throughout the procedure.

Minimal CO₂ insufflation is recommended as small bowel distention will decrease spiral advancement.

Irrigation using a water jet may help with lumen visualization and spiral advancement. Intermittent external abdominal compression is often helpful to facilitate engagement and advancement of the spiral segment.

17.3 General Withdrawal tips

Insufflation may be used at will at this time.

Although the scope may seem to be moving out of the patient quickly, it is important to keep holding the scope firmly.

Slow controlled withdrawal is the key. This is accomplished by backward rotation while maintaining the scope position and keeping the tip in motion

[figure not shown]
Clinical Investigation Plan

CIP Reference No.:2018-GI (OEKG) -01. The **SAMISEN** study - Final Version 02 - Date 23th April 2019

[figure not shown]
17.4 Antegrade Approach

17.4.1 Inserting the Scope

After passage of the bougie, the tip of the scope is advanced through the mouthpiece into proximal esophagus.

Rotation is started when the spiral segment is in the proximal pharynx. Begin with slow rotation with gentle pressure if needed, and the esophagus is intubated under direct visualization.

Note

If significant resistance is encountered during esophageal intubation, the endoscope should be removed and the esophagus should be assessed.

If no stricture is observed or motor stalls frequently, consider passage of a large bougie dilator (54-60 Fr) prior to reintroduction of the PowerSpiral.

A second attempt may be tried, with deflation of endotracheal balloon considered, but if stalling continues the procedure image is generated is smaller in caliber than the rotary

Clinical Investigation Plan

[figure not shown]
CIP Reference No.:2018-GI (OEKG) -01. The **SAMISEN** study - Final Version 02 - Date 23th April 2019

17.4.2 Passing through the Pharynx & Esophagus

[figure not shown]
The spiral segment is engaged in the upper esophageal sphincter and rotational advancement is continued using the forward foot switch.

The patient's neck is extended as needed to straighten the passage through the cervical esophagus as the rotating spiral section is less flexible than the remaining section of the scope.

Once the spiral section is past the cervical esophagus, the patient's neck no longer needs to be extended and may be returned to the usual position

Note

Gentle forward pressure is applied while the spiral segment is rotated slowly and intermittently using the foot switch facilitating intubation of the esophagus.

[figure not shown]
A decrease in the amount of resistance and torque required for advancement is an indicator that the cervical esophagus has been passed.

Clinical Investigation Plan

CIP Reference No.:2018-GI (OEKG) -01. The **SAMISEN** study - Final Version 02 - Date 23th April 2019

17.4.3 Passing through the Stomach

[figure not shown]
Upon entering the stomach, gastric contents should be aspirated and CO₂ insufflation should be kept to minimum.

While on the stomach, gentle pushing with rotation of the spiral segment is recommended for advancement.

When the insertion tube mark at 80cm is in the mouthpiece, the entire spiral segment is in the stomach.

Clinical Investigation Plan

CIP Reference No.:2018-GI (OEKG) -01. The **SAMISEN** study - Final Version 02 - Date 23th April 2019

